#### 7.3.2 Investigator's Assessment of Adverse Events

The determination of seriousness, severity, and causality will be made by an on-site investigator who is qualified (licensed) to diagnose adverse event information, provide a medical evaluation of adverse events, and classify adverse events based upon medical judgment. This includes but is not limited to physicians, physician assistants, and nurse practitioners.

Laboratory abnormalities will be reported as AEs if there is a 2 standard deviation increase above baseline.

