
 
Invasive Mechanical Ventilation / extracorporeal membrane oxygenation (ECMO):
 
Ventilator / ECMO use up to Day 29.
 
Incidence and duration of new mechanical ventilation or ECMO use during the study.
 
	
 
Days of invasive mechanical ventilation/ECMO (if applicable) up to Day 29.
 

 
Hospitalization
 
Duration of hospitalization (days).
 
	
 
Days of hospitalization as of Day 29 and day 120
 

Mortality 
 
15-day mortality
 
29-day mortality
 
120-day mortality
 
	
 
Date and cause of death (if applicable)
 

To evaluate the safety of CCP as compared to the control arm as assessed by:	• SAEs

 
Cumulative incidence of SAEs through Day 29.
 
Cumulative incidence of Grade 3 and 4 clinical and/or laboratory AEs through Day 29.
 
Transfusion associated adverse events
 
	
 
Grade 3 and 4 AEs
 
Grade 2 or higher AE's attributed to CCP
 

 
Exploratory Objectives
 
To evaluate the virologic efficacy of CCP
 
	

 
as compared to the control arm as assessed by:
 
Percent of subjects with SARS-CoV-2 detectable in nasal sample at Days 1,5,8,15
 
Quantitative SARS-CoV-2 virus in NP/MTN sample at Days 1,2,5,8,15
 
	
 
Qualitative and quantitative polymerase chain reaction (PCR) for SARS-CoV-2 in NP/MTN swab on Day 1,2,5,8,15 (while hospitalized)
 

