Finally, there are risks associated with any transfusion of plasma including transmission of transfusion transmitted viruses (e.g. HIV, HBV, HCV, etc.), allergic transfusion reactions, anaphylaxis to transfusion, febrile transfusion reaction, transfusion related acute lung injury (TRALI), transfusion associated cardiac overload (TACO), and hemolysis should ABO incompatible plasma be mistakenly administered. To minimize the risks of disease transmission, all plasma donors will be required to meet full allogeneic blood donation requirements as determined by FDA and the collection center. Donors are screened for behavioral risk factors for bloodborne infections using the standard blood donor history questionnaire (DHQ) and extensive testing for blood borne pathogens using FDA-licensed tests for blood product testing. In addition, donors will fulfill all FDA convalescent donor requirements which require a history of COVID19 illness (documented by positive COVID-19 test at time of illness OR positive COVID-19 serology) and complete resolution of symptoms at least 28 days prior to donation, or complete resolution of symptoms at least 14 days prior to donation with negative COVID-19 nasopharyngeal swab or molecular diagnostic test from blood[19].

A recent observational series described the safety of CCP administered to over 5000 hospitalized patients with COVID-19 infection. The incidence of adverse events in the day after plasma infusion was < 1% with only 2 of 36 events attributed to CCP by the treating clinician, suggesting a favorable initial safety signal and no clear evidence of ADE. [20]

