# 7.2 Definitions

1. **Adverse Event (AE):** Any untoward medical occurrence in a clinical investigation subject who has received a study intervention and that does not necessarily have to have a causal relationship with the study product. An AE can, therefore, be any unfavorable and unintended sign (including an abnormal laboratory finding, for example), symptom, or disease temporally associated with the use of the study product, whether or not considered related to the study product.

2. Serious Adverse Event (SAE): Any adverse event that results in any of the following outcomes:

- 1. Death
- 2. Life-threatening (immediate risk of death)
- 3. Prolongation of existing hospitalization
- 4. Persistent or significant disability or incapacity

5. Important medical events that may not result in death, be life threatening, or require intervention or escalation of care may be considered a serious adverse event when, based upon appropriate medical judgment, they may jeopardize the subject and may require medical or surgical intervention to prevent one of the outcomes listed in this definition. Examples of such medical events include allergic bronchospasm requiring intensive treatment in an emergency room or at home, blood dyscrasias or convulsions that do not result in inpatient hospitalization.

- 3. **Unexpected Adverse Event (UAE):** An adverse reaction, the nature or severity of which is not consistent with the investigator's brochure.
- 4. Serious and Unexpected Suspected Adverse Reaction (SUSAR): An adverse reaction, the nature of which is not consistent with the investigator's brochure with severity as defined by SAE above.
- 5. Unanticipated Problem (UP): Unanticipated Problem that is not an Adverse Event (e.g. breaches of confidentiality, accidental destruction of study records, or unaccounted-for study drug).
- 6. **Protocol Deviation:** Deviation from the IRB-approved study procedures. Designated serious and nonserious
- 7. Serious Protocol Deviation: Protocol deviation that is also an SAE and/or compromises the safety, welfare or rights of subjects or others

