# 7.3 Safety Reporting Requirements

#### 7.3.1 **Reporting Interval**

All grade 3 and 4 AE's, grade 2 AE attributed to study product and SAEs will be documented from the first administration of study product. These AEs and SAEs will be followed until resolution even if AEs extend beyond the study-reporting period. Resolution of an adverse event is defined as the return to pre-treatment status or stabilization of the condition with the expectation that it will remain chronic. At any time after completion of the study, if the investigator becomes aware of a SAE that is suspected to be related to study product.

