# Event severity will be graded using the DAIDS toxicity table

https://rsc.niaid.nih.gov/sites/default/files/daidsgradingcorrectedv21.pdf

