# 8 STUDY MODIFICATION

#### 8.1 Halting Criteria for the Study

The study enrollment and dosing will be stopped and an ad hoc review by the SMC will be performed if any of the specific following events occur or, if in the judgment of the study physician, participant safety is at risk of being compromised:

1. Death within one hour of plasma infusion

2. Occurrence of a life-threatening allergic/hypersensitivity reaction (anaphylaxis), manifested by bronchospasm with or without urticaria or angioedema requiring hemodynamic support with pressor medications or mechanical ventilation, TRALI, TACO.

- 3. One participant with an SAE associated with study product.
- 4. Two participants with a Grade 3 or higher lab toxicity for the same parameter associated with study product. (Grading will be assessed using DAIDS Toxicity Table https://rsc.niaid.nih.gov/sites/default/files/daidsgradingcorrectedv21.pdf)
- 5. An overall pattern of symptomatic, clinical, or laboratory events that the SMC considers associated with study product and that may appear minor in terms of individual events but that collectively may represent a serious potential concern for safety.
- 6. Any other event(s) which is considered to be a serious adverse event in the good clinical judgment of the responsible physician. This will be appropriately documented.

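### The 2 SD laboratory rule in 7.3.2 has no limb for falls, leaves its SD undefined, and is not reconciled with the grade-based adverse event rules

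*Combined protocol and SAP*

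**What the plan says.** The reporting trigger for laboratory values is one sentence in 7.3.2: "Laboratory abnormalities will be reported as AEs if there is a 2 standard deviation increase above baseline". It is the only numerical test in the protocol for when a laboratory value is reported as an AE.

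Six other places bear on the same question:

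- **7.2 (AE definition).** An AE can be "any unfavorable and unintended sign (including an abnormal laboratory finding, for example", with no direction stated. The SAE definition gives "blood dyscrasias or convulsions that do not result in inpatient hospitalization" among its examples.
- **7.3.1 (what is documented).** "All grade 3 and 4 AE's, grade 2 AE attributed to study product and SAEs will be documented".
- **7.3.3 (severity).** "Event severity will be graded using the DAIDS toxicity table".
- **3 and 5.1 (safety objective).** "Cumulative incidence of Grade 3 and 4 clinical and/or laboratory AEs through Day 29".
- **6.2.4 (analysis).** AE analysis is mainly descriptive, using DAIDS coding, and rates are compared between arms by Fisher's exact test.
- **8.1 (halting criterion 4).** "Two participants with a Grade 3 or higher lab toxicity for the same parameter associated with study product".

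The CBC is among the safety laboratory tests in 7.1.2. Table 1 in 5.4 schedules it, with an absolute lymphocyte count, at one baseline time and at follow-up.

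**The concern.** There are three defects in the 7.3.2 sentence.

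- **Direction.** It responds to increases only. For the cell counts in a CBC the harmful change is usually a decrease.
- **Undefined SD.** It could be the SD of repeat values within a patient, the SD of change, the SD between patients, or one implied by a reference range. Table 1 schedules one baseline set, so the scheduled baseline data cannot supply a within-patient SD. Two assessors could apply the rule differently to the same result.
- **No stated relation to the grade-based rules.** Section 7.3.1 selects by grade among things that are already AEs, while 7.3.2 says when a laboratory value is reported as one. A reader can reasonably take 7.3.2 as a gate in front of 7.3.1, or as an extra trigger beside it.

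At stake is the grade 3 and 4 laboratory AE count to Day 29 that is compared between arms. If the sentence acts as a gate, a severe fall in a cell count could be left out of that count in either arm.

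**Working it through.** The plan attaches no error rate or power to this rule, so there is no stated figure to reproduce. The only number is the 2 SD threshold. The calculations assume normal values and no true change unless stated.

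**Inputs**

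- Threshold: an increase of more than 2 SD over baseline (7.3.2).
- Baseline: one scheduled set (Table 1).
- Which SD: not stated, so a range is shown.
- Test-retest correlation ρ, for the between-patient reading: not in the documents; assumed 0.5 to 0.9.
- Sample size, for scale only: 50, randomized 1:1 (6.1).

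**Step 1. Chance of flagging a rise, per analyte per visit**

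| Meaning of SD | Formula | Result |
|---|---|---|
| SD of a single within-patient value | 1 − Φ(2/√2) = 1 − Φ(1.414) | 7.9% |
| SD of change | 1 − Φ(2) | 2.3% |
| Between-patient SD, ρ = 0.5 | 1 − Φ(2/√(2(1 − ρ))) = 1 − Φ(2) | 2.3% |
| Between-patient SD, ρ = 0.7 | 1 − Φ(2.582) | 0.5% |
| Between-patient SD, ρ = 0.8 | 1 − Φ(3.162) | 0.08% |
| Between-patient SD, ρ = 0.9 | 1 − Φ(4.472) | below 0.001% |

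The same sentence therefore gives anything from 7.9% to practically zero, depending on a definition that the protocol omits.

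**Step 2. Chance of flagging a real fall**

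Take SD as that of a single value. A true fall of s SD is flagged by the increase-only rule with probability 1 − Φ((2 + s)/√2).

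- s = 2: 1 − Φ(2.828) = 0.2%
- s = 3: 1 − Φ(3.536) = 0.02%

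A rule of the same size that looked both ways would flag these falls with probability 50% and 76%. Read alone, the sentence is in effect blind to falls.

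**Step 3. Several tests per patient (illustration)**

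All follow-up values of an analyte are compared with the same baseline, so they are not independent. Simulating 200,000 patients with a shared baseline and four follow-up visits gives at least one chance flag per analyte in 21.2% (SD of a single value) or 7.2% (SD of change). Treating visits as independent would give 1 − (1 − 0.0786)^4 = 27.9% for the first, which is too high. With 10 analytes, assumed independent, 91% or 53% of patients would have at least one flag, about 45 or 26 of 50. Both are upper-end figures. In Table 1, follow-up bloods to day 15 are limited to patients still in hospital, and CBC, renal and liver values are recorded only if taken in routine care.

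**Step 4. From flag to documented AE**

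A flagged value must also be grade 3 or 4, or grade 2 and attributed to study product, or serious, before 7.3.1 documents it. The DAIDS table is not reproduced and the documents give no distribution of laboratory values, so the number of chance rises that end up documented cannot be calculated.

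**Step 5. The two readings**

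- As a gate: falls do not become AEs, so they cannot be counted in the grade 3-4 endpoint, and the direction-free definition in 7.2 is contradicted.
- As a supplement: falls can enter through 7.2, 7.3.1 and 7.3.3, but 7.3.2 adds a second criterion that cannot be applied without an SD and does not match the grades used for the endpoint, analysis and halting rule.

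The sentence needs to change on either reading.

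**The case against.** The strongest reply is that 7.3.2 does not restrict anything. It says what happens if there is an increase; it does not say only if. The AE definition in 7.2 already admits any abnormal laboratory finding and cites blood dyscrasias as potentially serious, 7.3.1 and the safety objective are not limited to rises, and 7.3.2 itself leaves classification to a qualified clinician. This stands, and it rules out a conclusion that a reader might draw: that falls in cell counts can never be AEs. That follows only if the sentence is read alone or as a gate, and the documents do not settle which.

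Three other inferences also go too far.

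- **That halting criterion 4 is disabled.** Section 8.1 refers to graded laboratory toxicity associated with study product. It mentions neither AE status nor direction. Criterion 5 in 8.1 also covers patterns of laboratory events.
- **That haemolysis would be missed.** Section 4.1.2 names "hemolysis should ABO incompatible plasma be mistakenly administered", a risk tied to error, while 5.3.4 requires ABO-compatible product. Transfusion-associated events are a separate safety outcome, SAEs are documented regardless, and haemolysis may also show as a rise in the liver tests.
- **That most patients would have a false laboratory AE.** At 7.9% per test, 20 to 40 independent tests would give 81% to 96% of patients. That takes the highest of several possible rates, assumes the number of tests, ignores the shared baseline, and skips the grade filter in 7.3.1.

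The objection does not defend the sentence. If the grade-based rules govern, it serves no purpose and cannot be applied as written.

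**Conclusion.** The point holds as a defect in the laboratory AE reporting rule. That the rule looks upward only, leaves its SD undefined and has no stated relation to the grade-based rules can be read directly from the text and needs no assumption. The consequence for falls is conditional: they are lost from the grade 3-4 laboratory AE endpoint if 7.3.2 is applied as a gate, and not necessarily otherwise. The per-test chance-flag rates rest on normality and, for the between-patient reading, on the assumed correlations. They show that the rule is indeterminate; they do not predict a number of false AEs.

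The effect is confined to laboratory AE counts and their comparison between arms. The primary endpoint analysis and the sample size of 50 are untouched. The change should be made, but the trial's main conclusion does not depend on it.

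**What to change.** Delete the 2 SD sentence from 7.3.2. In its place state that laboratory abnormalities, whether increases or decreases, are graded with the DAIDS table and are documented as AEs when they worsen from baseline to grade 3 or 4, or to grade 2 and are attributed to study product, as in 7.3.1. SAEs remain documented as 7.3.1 already provides.

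Leave the general AE definition in 7.2 unchanged: the new sentence sets what is documented, not what an AE is. Reconcile 7.2, 7.3.1, 7.3.2, 7.3.3 and 8.1 so that they refer to the same grading; this needs no change to any halting threshold. For any scheduled test that the table does not grade, say how it will be handled.

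Adding a downward limb to the 2 SD rule would not be enough. The SD would still be undefined, and the chance-flag rate per comparison would double, from 2.3% to 4.6% (SD of change) or from 7.9% to 15.7% (SD of a single value).

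The cost is one replacement sentence and a consistency check. The grading table is already specified and the laboratory values are already scheduled, so no new data collection and no change to the sample size are needed.

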# 7.3.3 Assessment of Seriousness

- 1. Event seriousness will be determined according to the protocol definition of an SAE
- 2. Assessment of Severity

# Event severity will be graded using the DAIDS toxicity table

https://rsc.niaid.nih.gov/sites/default/files/daidsgradingcorrectedv21.pdf

### 7.3.4 Assessment of Association

- 1. The association assessment categories that will be used for this study are:
  - Associated The event is temporally related to the administration of the study product and no other etiology explains the event.
  - Not Associated The event is temporally independent of the study product and/or the event appears to be explained by another etiology.

2. The investigator must provide an assessment of association or relationship of AEs to the study product based on:

- Temporal relationship of the event to the administration of study product
- Whether an alternative etiology has been identified
- Biological plausibility
- Existing therapy and/or concomitant medications.

# 7.4 Safety Oversight

#### 7.4.1 Monitoring Plan

1. AE requiring reporting as per above and SAE will be reviewed by protocol team weekly, or more often if needed.

2. A Safety Monitoring Committee (SMC) composed of independent experts without conflict of interests will be established. The SMC will review the study before initiation, after enrollment of patient 5 and patient 15, and monthly thereafter until enrollment completed. The SMC will review study data, including unblinded data, to evaluate the safety, efficacy, study progress, and conduct of the study.

# 7.5 Study compliance with clinical trial requirements

1. Study will be conducted in accordance with GCP and ICH. Specifically, regular QC will be conducted to document the following:

- a. There is documentation of the informed consent process and signed informed consent documents for each participant
- b. There is compliance with recording requirements for data points
- c. All SAEs are reported as required
- d. Individual participant study records and source documents align
- e. Investigators are in compliance with the protocol
- d. Regulatory requirements as per Office for Human Research Protections (OHRP), FDA, and applicable guidelines (ICH-GCP) are being followed.

# 8 STUDY MODIFICATION

#### 8.1 Halting Criteria for the Study

The study enrollment and dosing will be stopped and an ad hoc review by the SMC will be performed if any of the specific following events occur or, if in the judgment of the study physician, participant safety is at risk of being compromised:

1. Death within one hour of plasma infusion

2. Occurrence of a life-threatening allergic/hypersensitivity reaction (anaphylaxis), manifested by bronchospasm with or without urticaria or angioedema requiring hemodynamic support with pressor medications or mechanical ventilation, TRALI, TACO.

- 3. One participant with an SAE associated with study product.
- 4. Two participants with a Grade 3 or higher lab toxicity for the same parameter associated with study product. (Grading will be assessed using DAIDS Toxicity Table https://rsc.niaid.nih.gov/sites/default/files/daidsgradingcorrectedv21.pdf)
- 5. An overall pattern of symptomatic, clinical, or laboratory events that the SMC considers associated with study product and that may appear minor in terms of individual events but that collectively may represent a serious potential concern for safety.
- 6. Any other event(s) which is considered to be a serious adverse event in the good clinical judgment of the responsible physician. This will be appropriately documented.

# 8.2 Halting Criteria/Rules for Subject Infusion:

Infusion of study drug will be halted if any of the following manifestations of anaphylaxis develop and will not be restarted:

- Skin or mucous membrane manifestations: hives, pruritus, flushing, swollen lips, tongue or uvula
- Respiratory compromise: dyspnea, wheezing, stridor, hypoxemia
- A decrease in systolic blood pressure to < 90 mmHg or >30% decrease from baseline or a diastolic drop of >30% from baseline.
- Tachycardia with an increase in resting heart rate to > 130 beats per minute; or bradycardia <40 that is associated with dizziness, nausea or feeling faint.

• Any other symptom or sign which in the good clinical judgment of the study clinician or supervising physician warrants halting the infusion. For example, the rapid onset of gastrointestinal symptoms, such as nausea, vomiting, diarrhea, and cramps, for instance, may be manifestations of anaphylaxis and may warrant an immediate halt prior to meeting full SAE criteria

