# 5.3 Study Population

# 5.3.1 Inclusion Criteria for Enrollment:

- 1. Patients ≥18 years of age
- 2. Hospitalized with COVID-19
- 3. Enrolled within 72 hours of hospitalization OR within day 14 from first signs of illness
- 4. Pulmonary infiltrates on chest imaging
- 5. Oxygenation of <95% on room air
- 6. Laboratory confirmed COVID-19

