# 5.3.6 Study drug administration

0. Drug will be administered within 24 hours of randomization

- 1. Infusion rate  $\leq$  500 mL/hour
- 2. Pretreatment to minimize transfusion reactions (e.g. acetaminophen, diphenhydramine) may be given at the discretion of the clinical care team.
- 3. If an AE develops during infusion, the infusion may be slowed or stopped as per investigator's decision.
  - Most reactions to plasma are relatively minor and the infusion can generally be continued. Infusion site burning and non-allergic systemic effects can generally be managed with slowing of the infusion. Infusion can generally be continued in cases of itching or hives after pausing the transfusion, administering antihistamines, and observing the patient for worsening.
  - Severe allergic reactions such as, bronchospasm and hypotension, generally require discontinuation of the infusion.

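### Sections 5.3.6 and 8.2 conflict on whether an infusion may resume after isolated hives or itching, and Section 8.2 does not define hypoxemia or dyspnea for patients who enter hypoxic

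*Combined protocol and SAP*

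**What the plan says.** Two sections govern what happens when a patient reacts during the infusion.

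**Section 5.3.6 (Study drug administration)** starts from discretion: "If an AE develops during infusion, the infusion may be slowed or stopped as per investigator's decision". It describes most plasma reactions as relatively minor. On skin reactions it says: "Infusion can generally be continued in cases of itching or hives after pausing the transfusion, administering antihistamines, and observing the patient for worsening". It adds that severe allergic reactions, with bronchospasm and hypotension as examples, generally require the infusion to be discontinued.

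**Section 8.2 (Halting Criteria/Rules for Subject Infusion)** is mandatory: "Infusion of study drug will be halted if any of the following manifestations of anaphylaxis develop and will not be restarted". Three of its items matter here:

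- Skin: "Skin or mucous membrane manifestations: hives, pruritus, flushing, swollen lips, tongue or uvula"
- Respiratory: "Respiratory compromise: dyspnea, wheezing, stridor, hypoxemia"
- Blood pressure: "A decrease in systolic blood pressure to < 90 mmHg or >30% decrease from baseline or a diastolic drop of >30% from baseline"

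**Section 5.3.1**, inclusion criterion 5, requires "Oxygenation of <95% on room air". Section 4.1.4 describes the target population as hypoxic and says that the study was amended to admit patients on high flow nasal oxygen as well as nasal cannula.

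**The concern.** A bedside stopping rule has to give one answer for one sign. Here a nurse or investigator who sees isolated hives or itching finds two answers. Under Section 5.3.6 the infusion may resume once the steps listed there have been taken. Under Section 8.2 it is over. This is a patient-safety matter first.

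It also touches conduct. Section 7.5 requires quality control to document that investigators comply with the protocol, yet resuming after hives complies with Section 5.3.6 and breaches Section 8.2. Treatment is a single unit (Section 5.3.4), so a permanent halt fixes the only dose that the patient will receive.

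The respiratory items raise a different question. In patients enrolled because they are hypoxic, staff need to know what change during the infusion triggers the halt, and Section 8.2 does not say.

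**Working it through.** No power, sample size or event count underlies this point, so the main check sets the texts side by side.

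**Step 1. Compare the instructions sign by sign.**

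| Sign during infusion | Section 5.3.6 | Section 8.2 | Result |
|---|---|---|---|
| Hives | Interrupt, treat, observe; resumption generally allowed | Halt; no resumption | Contradiction on resuming |
| Itching (pruritus) | Same as hives | Halt; no resumption | Contradiction on resuming |
| Hypoxemia, dyspnea | Not mentioned; only the general discretion for adverse events | Halt; no resumption | No opposite instruction; term undefined in 8.2 |
| Bronchospasm (5.3.6), wheezing (8.2) | Generally discontinue | Halt; no resumption | Same direction |

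**Step 2. Check whether scope removes the skin conflict.** Section 8.2 calls its list manifestations of anaphylaxis. However, one listed sign is enough. No severity grade, second organ system or prior diagnosis of anaphylaxis is required. The last item in the list lets clinical judgement add reasons to halt but not waive one, and it contemplates halting before an event meets full SAE criteria. Neither section refers to the other. The conflict stays.

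**Step 3. Check the respiratory items.** The blood pressure item has an absolute limit and a change from baseline, and the heart rate item has numeric limits. Hypoxemia and dyspnea have neither a limit nor a baseline. Entry requires saturation below 95% on room air, and only severe hypoxemic failure is excluded (Section 5.3.2, criterion 3). A reference value is available: vital signs are taken immediately before the infusion (Section 5.4, Table 1 footnote and Day 1 procedures), and the Section 3 data list places oxygen saturation under vital signs.

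**Step 4. What the skin conflict does to dose.** Inputs: about 250 mL per unit (Section 5.3.4), a rate of at most 500 mL/hour (Section 5.3.6), and a first in-infusion vital-signs check at 10–20 minutes (Section 5.4). As an illustration, assume a constant maximum rate and a reaction noted at that check:

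- Rate: 500 / 60 = 8.33 mL/min.
- Delivered by then: 8.33 × 10 = 83 mL to 8.33 × 20 = 167 mL.
- Share of the unit: 83/250 = 33% to 167/250 = 67%.

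Under Section 8.2 the dose stays there; under Section 5.3.6 it may go on to 250 mL. At a slower rate the share delivered by that check would be smaller.

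**Step 5. What it does to the analysis set.** Section 6.2.1 excludes only randomized subjects who do not initiate an infusion. A patient halted partway stays in under either reading. Volume received may change; membership does not. The Day 1 procedures record infusion start and end times but do not mention volume.

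**Step 6. How many patients.** The only reaction figure is in Section 4.1.2: adverse events in fewer than 1% of over 5000 convalescent plasma recipients in the day after infusion. Applied to all 50 subjects as an assumption, this gives fewer than 0.01 × 50 = 0.5 expected events. It is not specific to hives or itching, it does not cover control plasma, and the text does not describe how minor reactions were captured. It cannot serve as a count for this point.

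**The case against.** The best defence is that the two sections cover different events: Section 5.3.6 minor reactions, and Section 8.2 suspected anaphylaxis. Both begin by interrupting the infusion, so they part only on resumption, and Section 5.3.6 is hedged. It is fair that the disagreement is confined to resumption, and the sponsor may have intended that division. The text does not state it. A single skin sign satisfies Section 8.2 as written, and its bar on resumption allows no exception.

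A reader might also infer four stronger points, which the documents do not support:

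- **That the sections are opposed on low oxygen.** Section 5.3.6 never mentions low oxygen or dyspnea and nowhere says to continue when oxygen falls. At most, its general discretion sits beside a mandatory halt.
- **That every eligible patient already meets a halting sign.** Section 8.2 is triggered by signs that develop, which implies new onset. The entry criterion is measured on room air, so a patient on supplemental oxygen may not have low saturation at infusion. Dyspnea is not an entry criterion.
- **That hives and itching are the most common plasma reactions.** Section 5.3.6 calls most reactions relatively minor but does not rank them.
- **That the trial result is biased.** Both arms receive plasma under the same rules, and volume is not an endpoint. Section 5.3.4 concedes that nursing staff may not be blinded, so uneven application by arm is possible, but nothing shows it.

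**Conclusion.** The point holds in two parts.

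1. Sections 5.3.6 and 8.2 contradict each other on resuming an infusion after isolated hives or itching. This rests on the wording alone and is secure.
2. Section 8.2 leaves hypoxemia and dyspnea without a threshold or change from baseline, in a population that must be below 95% on room air to enter. This is a gap in definition. It is neither a conflict with Section 5.3.6 nor a criterion that all patients meet at entry.

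The contradiction should be removed because it sits in a bedside safety rule. For an affected patient it decides whether the only unit can be completed; under the illustrative assumptions above, the difference is between 33–67% of the unit and up to all of it. The number of such patients cannot be estimated from the documents and may be small. No effect on the primary comparison is shown.

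**What to change.** The sponsor should reconcile Sections 5.3.6 and 8.2 into one instruction for isolated skin reactions and use the same text in both. If the two sections are meant for different situations, each should say which situation it covers and refer to the other. Section 8.2 should also state how hypoxemia and dyspnea apply relative to the patient's status immediately before the infusion. Which clinical rule to adopt is for the sponsor to settle with the transfusion service and the Safety Monitoring Committee; no view is offered here.

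The cost is agreed protocol wording. The pre-infusion vital signs are already scheduled, so no new data collection is needed, and the sample size and analysis are unaffected.
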